#### 9.8.1. **Mathematical forms for success:**

$$P(\mu < 0 | y, y_0, \widehat{\alpha_0}(y, y_0, \lambda, k)) > 0.975$$

where y and  $y_0$  represent the pivotal data and prior data, respectively, the notation  $\widehat{\alpha_0}(y,y_0,\lambda,k)$  is used to denote that the estimate of the discounting parameter  $\widehat{\alpha_0}$ , which depends on the pivotal data, prior data, and the Weibull shape and scale parameters, and  $\mu = \mu_t - \mu_c$  represents the baseline-adjusted treatment effect of BP change comparing RDN and control groups. See section 9.9.3 for more details.

#### 9.8.2. Mathematical forms for futility:

$$\frac{\sum_{1}^{N_{rep}} I(P(\mu < 0 | y_{imp}) > 0.975)}{N_{rep}} < 0.05$$

Where  $y_{imp}$  is a single completed dataset after imputation,  $N_{rep}$  is the number of imputation simulations done and  $\mu = \mu_t - \mu_c$  represents the baseline-adjusted treatment effect of BP change comparing RDN and control groups where  $\mu_t$  and  $\mu_c$  are the baseline adjusted BP changes in the RDN and control groups respectively.

#### 9.8.3. **Futility imputation procedure**

For the futility calculation, we calculate the probability of futility based on the maximum study size of 300 subjects which means we have three types of subjects to consider:

- 1. Subjects who have reached their 3-month endpoint.
- 2. Subjects who are enrolled and have baseline blood pressure but have not reached their 3-month endpoint.
- 3. Subjects who have not been enrolled.

Imputation procedures will be used to impute the blood pressure change for subjects of type 2 and type 3 above.

For type 2 subjects we use the following procedure:

- 2.1 Construct the posterior predictive distribution for blood pressure change using type 1 subjects, incorporating the prior data.
- 2.2 Simulate samples from the predictive distribution to impute the missing values of blood pressure change for type 2 subjects, conditional on observed baseline blood pressure.

For type 3 subjects, we do the following:

- 3.1 Construct the posterior predictive distribution for blood pressure change using type 1 subjects, including the prior data.
- 3.2 Simulate baseline blood pressure for type 3 patients.
- 3.3 Simulate blood pressure change from the predictive distribution.
- 3.4 Impute blood pressure change for type 3 subjects, conditional on simulated baseline blood pressure.

We then combine the type 1 subjects with the imputed subjects from steps 2.2 and 3.4 into a single dataset and construct the endpoint using the BayesDP function. This procedure will be repeated for many datasets ( $N_{rep} > 1000$ ) and we calculate the number of times the alternative hypothesis is accepted. If the proportion of times the alternative hypothesis is accepted is less than 5%, stop enrollment due to futility.

The bayesDP package, version 1.3.2, is available on the Comprehensive R Archive Network (CRAN) [https://CRAN.R-project.org/].

#### 9.9. Evaluation of Objectives

The study will be considered successful if we meet both the primary safety and efficacy hypotheses.

#### 9.9.1. Primary Safety Endpoint

The primary safety endpoint of the study is the incidence of Major Adverse Events (MAE), defined as a composite of the following events through one month post-randomization (6 months for new renal artery stenosis):

- All-cause mortality
- End-stage Renal Disease (ESRD)
- Significant embolic event resulting in end-organ damage
- Renal artery perforation requiring intervention
- Renal artery dissection requiring intervention
- Vascular complications
- Hospitalization for hypertensive crisis not related to confirmed non-adherence with medications or the protocol
- New renal artery stenosis >70%

The primary safety analysis will be performed using the ITT population defined in 9.1.3.1.

#### 9.9.1.1. Primary Safety Endpoint Analysis

Medtronic is using a performance goal approach to power the primary safety endpoint.

The safety performance goal for the Major Adverse Event (MAE) rate was developed based on review of and comparison to event rates of other renal interventions. The review of renal intervention literature reported event rates of 3.6 to 17.2%. The reported events differed among the studies; however, for a subset of these studies, we could estimate rates for a composite of events similar to our protocol's MAE composite (see Table 1 below). The major adverse event rate from these studies was 7.1%.

The performance goal is set to be 7.1%, which is the meta-analysis rate from historical trials in Table 1. The primary safety null and alternative hypotheses are:

 $H_0$ :  $\pi$  ≥ 7.1% vs.

 $H_a$ :  $\pi < 7.1\%$ 

where  $\pi$  is the MAE rate for patients undergoing renal denervation. Under the assumption that the true rate is 3.5%, and using a one-sided 0.05 level of significance, an evaluable sample size of 253 renal denervation patients yields 80% power to reject the null hypothesis in favor of the alternative. The exact binomial test was used for the sample size calculation for the primary safety endpoint hypothesis.

In other words, the primary safety endpoint hypotheses is designed to show whether the true MAE rate is lower than 7.1%. Compared to the literature reported event rates for renal intervention, we believe that these thresholds are appropriate for demonstrating safety of the device given the expected performance rates of similar renal intervention trials, particularly when balanced with the expected blood pressure reductions.

Medtronic proposes multiple sources of study patients as shown in Table 2 below to ensure 253 patients treated with the Symplicity Spyral catheter (including branch treatment) are available for analysis. The first 253 subjects with evaluable safety data from the sources in Table 2 will be used to perform the primary safety endpoint analysis.

With a sample size of 253 and a one-sided significance level of 0.05, a maximum of 11 subjects with MAE will enable us to meet the safety primary endpoint, resulting in an event rate of 4.3% with a one-sided 95% upper confidence bound of 7.09% using the exact binomial method.

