### **SPYRAL HTN-OFF MED 80 PATIENT COHORT**

SPYRAL HTN-OFF MED is a multicenter, international, single-blind, randomized, sham-controlled trial. Eligible patients are drug-naive or discontinue their antihypertensive medications. Patients with an office systolic blood pressure (SBP) of 150 mm Hg or greater and less than 180 mm Hg, office diastolic blood pressure (DBP) of 90 mm Hg or greater, and a mean 24-h ambulatory SBP of 140 mm Hg or greater and less than 170 mm Hg at second screening, have renal angiography and are randomly assigned to renal denervation or sham control. Patients, caregivers, and those assessing blood pressure are blinded to randomization assignments.

While study enrollment is ongoing, data from the initial 80 patients with 3 months follow up from the SPYRAL HTN-OFF MED study was presented at ESC Congress in August 2017. Concurrently, an article presenting the data was published in the Lancet. A brief summary of the SPYRAL HTN-OFF MED data is provided below.

[figure not shown]
The primary endpoint, change in 24-h blood pressure at 3 months, was compared between groups. Drug surveillance was done to ensure patient compliance with absence of antihypertensive medication. The primary analysis was done in the intention-to-treat population. Safety events were assessed at 3 months.

Between June 25, 2015, and January 30, 2017, 353 patients were screened. 80 patients were randomly assigned to renal denervation (n=38) or sham control (n=42) and followed up for 3 months at 21 centers in the USA, Europe, Japan, and Australia.

There were no major adverse events in either group. No major procedural or clinical safety events were observed in either the renal denervation or sham control groups throughout the 3 months. Specifically, there were no deaths or occurrences of myocardial infarction, stroke, major bleeding, serum creatinine elevation greater than 50%, significant embolic events, vascular complications, renal artery re-intervention, new or worsening renal failure, or hypertensive emergency or crisis.

Office and 24-h ambulatory blood pressure decreased significantly from baseline to 3 months in the renal denervation group (Figure 3). No significant changes were seen in the sham-

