***Medtronic Confidential***

---

$H_0: \pi \geq 7.1\%$  vs.

$H_a: \pi < 7.1\%$

where  $\pi$  is the MAE rate for patients undergoing renal denervation. Under the assumption that the true rate is 3.5%, and using a one-sided 0.05 level of significance, an evaluable sample size of 253 renal denervation patients yields 80% power to reject the null hypothesis in favor of the alternative. The exact binominal test was used for the sample size calculation for the primary safety endpoint hypothesis.

In other words, the primary safety endpoint hypothesis is designed to show whether the true MAE rate is lower than 7.1%. Compared to the literature reported event rates for renal intervention, it is believed that these thresholds are appropriate for demonstrating safety of the device given the expected performance rates of similar renal intervention trials, particularly when balanced with the expected blood pressure reductions.

Medtronic proposes multiple sources of study subjects as shown in Table 10 below to ensure 253 patients treated with the Symplicity Spyral catheter (including branch treatment) are available for analysis. The first consecutively randomized 253 subjects with evaluable safety data from the sources in Table 10 will be used to perform the primary safety endpoint analysis.

With a sample size of 253 and a one-sided significance level of 0.05, a maximum of 11 subjects with MAE will enable us to meet the safety primary endpoint, resulting in an event rate of 4.3% with a one-sided 95% upper confidence bound of 7.09% using the exact binomial method.

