# 8. Determination of Sample Size

This study will be conducted as an adaptive Bayesian trial with an informative prior. A Bayesian power prior approach [3,4] in conjunction with a discount function will be used to incorporate the prior data. The discount function reduces the strength of the prior data if disagreements are observed with the pivotal data.

The prior data consists of the first consecutively randomized 80 patients in the SPYRAL HTN-OFF MED study, the results from these 80 subjects have been analyzed and published [6]. The weight of the prior data will be adjusted using a discount function, which scales from 0 to 1, according to the similarity of the prior and pivotal data. This discount function adjusts the amount of weight the prior receives. This prevents the use of an informative prior where exchangeability issues are present (e.g., the prior and pivotal data are quite different). This discount function approach was proposed by the Medical Device Innovative Consortium (MDIC) working group and is a collaborative effort between FDA and industry through the MDIC [1,2]. If the analyses show a high level of agreement for pivotal data compared to the prior, the prior will be weighted at or near 100%. If the pivotal data perform worse than or much better than the prior, then the prior will receive very little or zero weight. The Bayesian adaptive design is set up to enroll patients until a sufficient sample size is achieved to have high probability of meeting the endpoint.

The sample size of the study will vary from 210 to 300 subjects with 3-month follow-up due to the adaptive nature of the trial. This will require approximately 247 to 353 randomized subjects to account for a 15% attrition at 3-months. Based on this attrition rate, the interim analyses will take place after the 210th and 240th subjects have completed 3-month follow-up, with a maximum study size of 300 subjects if the study does not stop at either interim look. The actual rate of attrition will dictate the available sample size for analyses. At each interim analysis, enrollment may be stopped for efficacy or futility.

Simulations of trial design operating characteristics performed to demonstrate control of type I error & power are presented in section 9.9.6 for the primary and secondary efficacy endpoints.

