**Table 2: Study Sources of Patients for Primary Safety Endpoint Data** 

Study
SPYRAL HTN-OFF MED prior data (First 80
Subjects)
Randomized 1:1 to RDN:CONTROL
SPYRAL PIVOTAL – SPYRAL HTN-OFF MED
Randomized 1:1 to RDN:CONTROL
SPYRAL HTN-ON MED First 106
Randomized 1:1 to RDN:CONTROL
SPYRAL HTN ON MED Extension
Randomized 2:1 to RDN:CONTROL
SPYRAL HTN-OFF MED Crossovers (from
prior and pivotal)
SPYRAL HTN-ON MED Crossovers (from first
106 and Extension subjects)

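### The primary safety test counts 38 denervated pilot patients already reported free of major adverse events; given those results, the chance of passing at a true 7.1% rate is up to about 16%, and the stated 0.05 holds only if all 253 outcomes were unknown

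*SAP*

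**What the plan says.** SAP 9.9.1.1 and Protocol H.2 compare the MAE rate in denervated patients with a fixed goal: "The performance goal is set to be 7.1%, which is the meta-analysis rate from historical trials in Table 1". The design line reads "Under the assumption that the true rate is 3.5%, and using a one-sided 0.05 level of significance", and "an evaluable sample size of 253 renal denervation patients yields 80% power to reject the null hypothesis in favor of the alternative". At most 11 patients with an MAE meets the endpoint; 11 of 253 is 4.3%, with an exact one-sided 95% upper bound of 7.09%.

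On who enters, the SAP says "The first 253 subjects with evaluable safety data from the sources in Table 2 will be used to perform the primary safety endpoint analysis". Protocol H.2 adds the order: "The first consecutively randomized 253 subjects with evaluable safety data". The first source in SAP Table 2 is "SPYRAL HTN-OFF MED prior data (First 80" subjects), and Protocol Table 10 lists the same cohort.

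On what was known, SAP section 8 says of this cohort that "the results from these 80 subjects have been analyzed and published". Protocol B.1.2 gives 38 patients randomized to denervation and 42 to sham, followed for 3 months, and reports: "There were no major adverse events in either group".

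The endpoint runs to one month after randomization, except that new renal artery stenosis above 70% counts to 6 months (SAP 5.1).

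**The concern.** A binomial reference distribution with 253 trials treats all 253 outcomes as open when the rule is fixed. Under the protocol's ordering by randomization, the OFF MED pilot (June 2015 to January 2017) is among the earliest sources, so its denervated patients fall inside the 253. The SAP that states the rule also states that this cohort had been analyzed and published. For these patients most of the endpoint was no longer open.

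The efficacy analysis treats the same cohort differently. It is discounted where it disagrees with the pivotal data, and SAP Tables 3 and 4 enter its observed means and standard errors as inputs to the simulations behind the type I error in Table 5. The efficacy error rate is therefore given with the pilot taken as observed. The safety test adds the pilot at full weight, with no discount, no conditional error rate and no result without it.

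At stake is what a pass means. Suppose 11 events occurred, all outside the pilot. The plan would report 4.3% with a bound of 7.09% and declare the goal met, although the patients who supplied the new information would have a bound above 7.1%.

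**Working it through.** **Inputs.** Goal 7.1%, assumed true rate 3.5%, one-sided 0.05, n = 253, limit 11 (SAP 9.9.1.1). Pilot: 38 denervated, no MAE to 3 months (Protocol B.1.2). It is assumed that all 38 were treated and evaluable; this is varied below.

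**The plan's own figures.** With X ~ Binomial(253, p):
- P(X ≤ 11 | p = 0.071) = 0.0496. A limit of 12 would give 0.085, so 11 is the correct maximum.
- P(X ≤ 11 | p = 0.035) = 0.820, against the stated 80%.
- Exact bound at 11/253: the 0.95 quantile of Beta(12, 242) = 7.09%.

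All three are in order. The extra two points of power come from binomial discreteness: 253 is the smallest n that reaches 80% (252 gives 73.0%).

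**Conditioning on the pilot.** With 38 outcomes fixed at zero, 253 − 38 = 215 are open and the rule is X ≤ 11 with X ~ Binomial(215, p):
- P(X ≤ 11 | 215, 0.071) = 0.158.
- Exact bound at 11/215 (5.1%) = 8.3%.

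The two error rates agree with each other, because 0.0496 is the average over all pilot results:

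| Pilot events | Probability at 7.1% | Chance of then passing |
|---|---|---|
| 0 | 0.061 | 0.158 |
| 1 | 0.177 | 0.098 |
| 2 | 0.250 | 0.055 |
| 3 | 0.229 | 0.028 |

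The first row is the one that was reported.

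**Stenosis still open.** Let s be the share of the 7.1% that is stenosis arising after the pilot's 3-month report. The documents give no split, so s is an assumption. A pilot patient event-free so far has remaining risk q = 0.071s / (1 − 0.071(1 − s)). The chance of passing is the sum over x of P(Bin(38, q) = x) × P(Bin(215, 0.071) ≤ 11 − x).

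| s | q | Chance of passing at 7.1% |
|---|---|---|
| 0 | 0 | 15.8% |
| 10% | 0.0076 | 14.1% |
| 25% | 0.0187 | 11.9% |
| 50% | 0.0368 | 9.0% |
| 100% | 0.071 | 5.0% |

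**Fewer evaluable pilot patients.** With 35 instead of 38 (and s = 0), P(X ≤ 11 | 218, 0.071) = 0.146.

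**Limit for unreported patients alone.** With 215, 8 events give size 0.028 and a bound of 6.6%; 9 give size 0.055 and a bound of 7.2%. The limit is therefore 8. Power is 66% at a true 3.5%, and 99.6% at 1.4%, the rate Protocol B.1.1 quotes for SYMPLICITY HTN-3.

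**The case against.** The strongest reply is that nothing is miscalculated. The 0.05 is the unconditional size of an exact test and it is correct. The SAP defines its parameter as the rate in patients undergoing denervation, not in those enrolled after the pilot, and Table 2 labels the pilot openly as prior data. Pooling it is a disclosed choice. This stands as a reason not to call 0.05 an arithmetic error and not to discard the pooled test. It does not make the unconditional size the right description of a rule written down with the pilot in hand, and the SAP does not describe its efficacy error rate that way.

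It is also fair that zero MAEs in the pilot are not fully established for this endpoint. The 3-month report precedes the 6-month duplex scan, and its itemized list does not name stenosis, dissection or perforation. Hence a range, with 16% as its upper end.

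Two stronger readings are tempting. A reader might infer a 39% chance of passing, since the ON MED pilot is also a source and its 38 denervated patients are reported free of MAEs to 6 months: 253 − 76 = 177, and P(X ≤ 11 | 177, 0.071) = 0.392. That applies only if those results were known when the rule was fixed. The SAP version history carries no dates in the text available, and the SAP calls only the OFF MED results analyzed and published. A reader might also infer that the device is unsafe. The protocol's summary of the first interim analysis points the other way: no major safety events at 1 month, with 166 randomized to denervation. Of these, 166 − 38 = 128 are outside the pilot, and 0/128 has an exact upper bound of about 2.3%, leaving aside 6-month stenosis.

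**Conclusion.** The point holds as a statement about the error rate. The 0.05 level describes 253 unseen patients. Given the reported OFF MED results, the chance of passing at a true 7.1% rate is up to about 16%: 9% to 14% if late stenosis makes up an assumed 50% to 10% of MAEs, and 14.6% if only 35 pilot patients are evaluable and no stenosis is open. It returns to 5% only if every MAE is late stenosis. The 39% figure is not supported, because the documents do not show that the ON MED results were known when the rule was set.

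This rests on the protocol's ordering by randomization and on SAP section 8, which shows that the current SAP postdates the pilot results. It does not show that the primary test must be replaced. It is a figure behind one of the two success hypotheses that should be restated and accompanied by a second bound, which is short of a fault that invalidates the test.

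**What to change.** Keep the prespecified test on the pooled 253 patients with its limit of 11, and make two additions to SAP 9.9.1.1 and Protocol H.2.

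1. State that 0.05 is the unconditional size and give the error rate conditional on the reported pilot results: 0.158 with 38 evaluable and nothing open, with the stenosis range beside it. This brings safety into line with the efficacy simulations, which take the prior data as given.
2. Prespecify the exact MAE rate and one-sided 95% upper bound in denervated patients not previously reported, shown next to the pooled result. Base any claim that new patients meet the 7.1% goal on that bound. With 215 such patients, 8 or fewer events puts it below 7.1%; 11 events would give 8.3%.

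The cost is wording and one extra exact interval, with no new patients. The stated error rate becomes less favourable, and the new-patient bound has less power than the pooled test: 66% against 82% at a true 3.5%, though above 99% at 1.4%.

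Making the new-patient bound the primary test would impose that loss of power on the success criterion. Refilling the 253 without the pilot would keep the power but needs 38 replacements from the other listed sources, and the documents do not show how many are available. Neither step is required to correct the stated figure.

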**Table 2: Study Sources of Patients for Primary Safety Endpoint Data** 

Study
SPYRAL HTN-OFF MED prior data (First 80
Subjects)
Randomized 1:1 to RDN:CONTROL
SPYRAL PIVOTAL – SPYRAL HTN-OFF MED
Randomized 1:1 to RDN:CONTROL
SPYRAL HTN-ON MED First 106
Randomized 1:1 to RDN:CONTROL
SPYRAL HTN ON MED Extension
Randomized 2:1 to RDN:CONTROL
SPYRAL HTN-OFF MED Crossovers (from
prior and pivotal)
SPYRAL HTN-ON MED Crossovers (from first
106 and Extension subjects)

#### 9.9.2. Secondary Safety Objectives

The following secondary safety endpoints will be assessed:

 Acute/Procedural Safety Secondary Endpoints – Compared Between Groups at 1 Month Post-Procedure:

- Significant embolic event resulting in end-organ damage
- Renal artery perforation requiring intervention
- Renal artery dissection requiring intervention
- Vascular complications
- End-Stage Renal Disease
- ≥40% decline in eGFR
- New myocardial infarction
- New stroke
- Renal artery re-intervention
- Major bleeding according to TIMI definition (i.e. intracranial hemorrhage, ≥5g/dl decrease in hemoglobin concentration, a ≥15% absolute decrease in hematocrit, or death due to bleeding within 7 days of the procedure)
- Increase in serum creatinine >50% from Screening Visit 2
- New renal artery stenosis >70%, confirmed by angiography and as determined by the angiographic core laboratory
- Hospitalization for hypertensive crisis not related to confirmed non-adherence with medications or the protocol
- Chronic Safety Secondary Endpoints Compared Between Groups at 3, 6, 12, 24, and 36 Months Post- Randomization:
  - Composite Safety Endpoint, defined as a composite of the following events:
    - All-cause mortality
    - End-Stage Renal Disease (ESRD)
    - Significant embolic event resulting in end-organ damage
    - Renal artery perforation requiring intervention
    - Renal artery dissection requiring intervention
    - Vascular complications
    - Hospitalization for hypertensive crisis not related to confirmed non-adherence with medications and/or the protocol
    - New renal artery stenosis >70%, confirmed by angiography and as determined by the angiographic core laboratory
  - ≥ 40% decline in eGFR
  - Increase in serum creatinine >50% from Screening Visit 2
  - New myocardial infarction
  - New stroke
  - Renal artery re-intervention
  - Major bleeding according to TIMI definition (i.e. intracranial hemorrhage, ≥5g/dl decrease in hemoglobin concentration, a ≥15% absolute decrease in hematocrit, or death due to bleeding within 7 days of the procedure)
  - Hospitalization for hypertensive crisis not related to confirmed non-adherence with medication and/or protocol.
  - Summary of health related Quality of Life (HRQoL) analysis based on reporting measures using accepted QoL instruments (EQ5D and SF36).

All the safety endpoints will be adjudicated by the Clinical Events Committee (CEC). The following algorithm will be used to evaluate the safety event rates: The denominator will include all subjects who either had a CEC adjudicated event prior to the time of interest (180 days for 6 months events, for example), or had last contact date that is beyond the lower window of the follow up (166 days for 6 month events, for example). The numerator will include all subjects who had CEC adjudicated events up to the time of interest (180 days for 6 months events, for example).

The secondary safety endpoints, out to 6-months follow-up, will be compared between treatment groups using Fisher's exact test. Two-sided 95% confidence intervals of the difference between treatment groups will also be presented.

After 6-months follow-up, control subjects may crossover (undergo renal denervation), and secondary safety endpoints will be summarized by group (RDN, Crossovers, Non-Crossovers). RDN vs. Crossover vs. Non-Crossover groups will be compared out to 36 months post-procedure for the RDN and Non-Crossover groups and out to 24 months for the Crossover group using chi-square tests for categorical data and ANOVA for continuous data.

The secondary safety analyses will be performed using the ITT population defined in section 9.1.3.1.

